We conducted a pilot RCT at the same site to compare the program with usual care (at least 2 visits with a Nurse Educator). We enrolled 77 persons who started or changed ART within the previous 6 months. Participants were randomized 2:1 to LN (n = 51) or standard care (n = 26) and completed baseline (T1), 6 week (T2), and 12 week (T3) assessments and monthly pill counts (PC). Blood draws measured plasma antiretroviral medication trough levels at 12 weeks, an innovative measure of adherence. Significance for this small sample pilot was set at $p \leq .1$. Mean age was 44.7 yrs; 65% were male; 88% were African American; participants were HIV-infected for 9.6 years (median). Median monthly income was \$674. At T3 we found adherence declined over time for both groups; however the drop was greater for the control group compared to the LN group: 67% (14 of 21) of controls but only 52% (22 of 42) of intervention subjects dropped below baseline values (NS). While not statistically significant, PCs at T3 were higher for intervention participants (77.8% vs. 70.6%). Also at T3, 80.5% of LN subjects vs. 72.7% of controls had antiretroviral plasma trough levels at or above therapeutic range (n=63, NS). CD4 and viral load (VL) were analyzed using multilevel mixed models. There was a larger proportion of LN group with undetectable VL log (≤ 1.88) at all time points. VL log (inverse transformed) yielded a significant group by time interaction ($t=1.890$, $p=0.067$, and model deviance change $\chi^2=3.07$, $df=1$, $p=0.08$) for the LN. No significant differences were seen for CD4. Adherence self-efficacy scores improved in the LN group from T1 to T3 ($\chi^2=5.1$, $df=2$, $p=0.080$). No significant changes were seen for the control group ($\chi^2=2.6$ ($df=2$), $p=0.273$). Wilcoxon pairwise post hoc tests using Bonferroni corrected alpha=0.033 indicated significant differences between T1 and T3 ($Z=-2.39$, $p=0.017$) and between T2 and T3 ($Z=-2.39$, $p=0.017$). Self-efficacy had the largest effect sizes seen in this study; the largest changes occurred between T1 and T3 indicating that the study should be run longer to establish sustainable improvements. For the LN group, ART self-efficacy scores increased by 6.05 ($sd=12.97$) for an estimated effect size of 0.47, a medium effect size. Participants with higher CES-D scores (depressive symptoms) at T1 were 1.08 times more likely ($p=0.03$) to have drug trough levels below the therapeutic range at T3. There were no differences between or within groups in numbers of symptoms or symptom distress. Small sample size and short duration of follow-up limit our results. All

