c.5 Potential impact The challenge for HIV+ persons is to achieve and maintain high levels of adherence to medications, some of which have rigorous dosing schedules and burdensome side effects, amidst the barriers encountered living in a rural area. The challenge for health care professionals, then, is to provide consistent and easy access to a high level of education and motivational support to PLWHA in rural areas where resources are limited and barriers such as stigma, travel distance, transportation,

and shortages of trained health care providers may preclude regular in-person visits with clinical staff for ART education and follow-up. We will use widely available smart phone and mobile app technology to test a practical adherence strategy that could potentially sustain the long-term benefit of ART among PLWHA in rural Georgia by improving self-efficacy for ART adherence. Should the LN app show promising results, this strategy, unlike many others that have been previously evaluated, could be rapidly scaled up to address the needs of rural populations nationwide. It can be easily incorporated into routine clinical ART adherence counseling. Because it is self-administered, training can occur during a routine clinic visit or at home. There is no visible identifying or stigmatizing characteristics. PLWHA in rural areas who use this program can blend in easily anywhere that portable playing devices and cell phones are used without fear of loss of confidentiality. Equipment that is increasingly ubiquitous (a smart phone with mobile apps) enhances the sustainability and as new information becomes available, updates can easily be downloaded to the app. With its focus on technology, the project helps bring rural health care into the 21st century³¹ and also exposes rural PLWHA to mobile technology; something they clearly desire. The development of self-management programs into a mobile app could also be adapted to improve adherence in other aspects of HIV-disease management. The potential impact of this project is major, and could transform the delivery of self-management and adherence education.

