private information outside the group. There is a remote risk of anxiety or stress related to the discussion content. For the **RCT** there is a very remote risk of injury from clipping hair samples. Completion of the assessments and participation in the interventions are free of risks for physical harm. However, both the assessments and the intervention may raise personal issues, which may be troublesome to some of the participants. Some participants may feel anxious as a result of dealing with these issues. Use of the mobile app and text messaging could display private information. These risks will be explained in the consent form. All study staff will be trained in the mental health aspects of HIV/AIDS, how to recognize and deal with emotional or behavioral problems, including anxiety, as they arise, and will be asked to report all adverse events to the principal investigator.

f.2 Procedures to reduce Risk

f.2.a. Recruitment and Consent Procedures

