Satisfaction (Aim 1) Two assessments will be conducted and analyzed to determine participant satisfaction with the mobile app in general, LN program and interactive manual. Both times, we will ask questions about likeability, usage rates, ease of use, acceptability, satisfaction, relevance, favorite song, understandability, and suggestions for improvement. The first assessment will entail observations and discussions with rural PLWHA while using the mobile app in focus group format. Observations and discussions will be recorded and content analyzed for themes, which will inform final revisions to the LN app. The second feasibility analysis will be the Program Evaluation Survey at the end of the study. Scaled responses to questions related to the above criteria will be analyzed using descriptive statistics and written comments will be entered into nVivo software and content analyzed for themes. We will also describe and evaluate the usage data from the web application designed to track app usage. We will determine average usage patterns and compare between groups (LN vs. EP).

Outcomes (Aim 2) All covariates will be evaluated to determine if any differences exist at baseline between the 2 groups (LN and EP), as well as testing for interactions (moderation) between groups and time. Inter-correlation among the covariates will also be evaluated. Multicollinearity diagnostics (variance inflation factors, tolerance, condition index) will be used to determine which covariates should remain in the subsequent models. MLM longitudinal models as detailed above will be used for each outcome (H1: adherence, H2: drug levels, and H3: CD4, viral load, drug resistance) to test differences between the 2 groups (group main effect), test for changes/differences from baseline to 3, 6 and 9 month (time main effect) and test for group by time effects (i.e. changes from baseline that are differences between the 2 groups) adjusting for significant covariates/moderators as needed. Appropriate link functions (e.g. logit, Poisson, other) will be assessed for each outcome within the MLM.

Exploratory outcome, mediators and moderators (Aim 3) Symptoms and symptom management scores will be examined using MLM as described above. Self-efficacy, outcome expectancy and personal goals are mediators in our model and meet the criteria for mediators as defined by Baron and Kenny⁴⁴

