As mentioned above the potential risks from this study are minimal and we had no adverse events during the pilot study of the Music Project (n = 77). Therefore, adverse events and clinical outcomes will be monitored by the Principal Investigator (PI) in collaboration with the Co-Investigators (Co-I's). All study staff will be trained to recognize and report adverse events immediately to the PI who will report them to the Emory University IRB. Data management will be done by the study project coordinator who will assure quality and security of the data from start through conclusion of the project and will notify the PI of any breaches in data security. S/He will also provide real-time checks of forms-based data, and at least monthly monitoring of data quality and completeness.

The PI will review the following indicators on a monthly basis.

- a. adherence to the goals for recruitment and retention;
- b. adherence to the study protocols;
- c. cumulative data for evidence of study related adverse events;
- d. quality, accuracy, completeness, and timeliness of the data collected thus far;
- e. factors that could affect the outcome or compromise participant/data confidentiality;
- f. other factors outside the study (e.g., therapeutic developments, agency related policies) that could impact the safety of participants or the ethical conduct of the study.

In general, if problems arise, the PI will consult with Co-I's and the IRB to make possible recommendations:

- a. continue the study without change;
- b. modifications to the study protocol;
- c. suspension or early termination;
- d. alternative approaches to consider (e.g., if there is a failure to accrue participants as anticipated, such as addition of another site).

If a breach in data or individual confidentiality, a study related adverse event, or a significant protocol violation occurs, the PI will contact the IRB as soon as possible to discuss and make recommendations for action.

5. Confidentiality

See 'F' above.

6. Informed consent

The informed consent for each part of the study has been downloaded to the e-IRB application.

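### The pilot's zero adverse events say nothing about app and text privacy risk, and no measure described asks participants about unwanted disclosure or other study-related harm

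*Combined protocol and SAP*

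**What the plan says.** **Monitoring (section 4).** Two reasons are given. One is a judgement of low risk: "As mentioned above the potential risks from this study are minimal". The other is experience so far: "we had no adverse events during the pilot study of the Music Project (n = 77"). The next sentence concludes from them that the PI, with the co-investigators, will monitor adverse events. Trained staff recognize events and pass them to the PI, who reports to the IRB. Each month the PI reviews accumulating adverse event information and anything that might compromise confidentiality. A breach leads to contact with the IRB.

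**The pilot (Background, b. Preliminary Studies).** Its purpose was to "compare the program with usual care (at least 2 visits with a Nurse Educator"). "Participants were randomized 2:1 to LN (n = 51) or standard care (n = 26"), and they "completed baseline (T1), 6 week (T2), and 12 week (T3) assessments and monthly pill counts (PC"). Adherence change at 12 weeks is reported for 42 LN and 21 control participants.

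**The app (a. Specific Aims, Aim 1).** Turning LN into a mobile application is a task of the present project. The focus groups held before the pilot used MP3 players. The delivery device in the pilot RCT is not stated.

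**Risk and prevention.** For the RCT, f.1 says "Use of the mobile app and text messaging could display private information". Section f.2.b answers with preventive steps: no HIV terms in videos or texts, code words, a privacy check at the start of calls, a neutral project name, and advice to use the manual in private.

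**What participants are asked.** Sections d.2.1 and e list adherence, symptoms, depression, self-efficacy, attitudes, goals, demographics, health literacy, and app acceptance and use. The satisfaction assessments in h.2.b cover "likeability, usage rates, ease of use, acceptability, satisfaction, relevance, favorite song, understandability, and suggestions for improvement", with written comments analysed for themes. Section e says that copies of the instruments are in the IRB application.

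**The concern.** The route by which events reach the PI depends on staff seeing or hearing of them. That works for hair clipping, which staff do in person. It works poorly for a relative or housemate who sees a message or a screen at home. ACASI administers most items, pill counts are done by app or telephone, and follow-up assessments may be by phone, so staff may have little occasion to learn of such an event. The f.2.b measures are meant to prevent disclosure. They do not show when prevention has failed.

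The pilot cannot fill this gap, because it came before the app. If participants are not asked, a low harm count at the end could reflect either safety or silence, and the report could not tell the two apart. The trial would then have little evidence for or against the advantage claimed in c.5, where users are said to blend in "without fear of loss of confidentiality".

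**Working it through.** **1. Reproduce the plan's count.** 51 (LN) + 26 (standard care) = 77. The figure in section 4 is correct as a count of pilot participants.

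**2. What zero events can exclude.** The documents give no confidence limit. For zero events in n people, the exact one-sided 95% upper limit is 1 − 0.05^(1/n), and the two-sided Clopper-Pearson limit is 1 − 0.025^(1/n).

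| Denominator | n | One-sided 95% | Two-sided 95% |
|---|---|---|---|
| Whole pilot | 77 | 3.8% | 4.7% |
| Randomized to LN | 51 | 5.7% | 7.0% |
| LN with 12-week adherence data | 42 | 6.9% | 8.4% |

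These limits concern any adverse event over about 12 weeks. The row for 51 assumes that all 51 were fully observed. The row for 42 shows the limit if only those with 12-week adherence data were. As a check on how little a zero count says, a true 12-week risk of 2% would give no events in 51 people with probability 0.98^51 = 0.36.

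**3. What the pilot says about app and text privacy.** Aim 1 builds the app in this project, so the number of pilot participants exposed to it is taken as 0. With n = 0 there is no upper limit to compute. The pilot description mentions no study text messages, so it supplies no information on those either. The limits in step 2 therefore do not carry over to this risk.

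**4. Match the named risk to a source of data.**

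| Described source | Would it pick up disclosure away from staff? |
|---|---|
| Staff recognition and report (f.1, section 4) | Only if the participant raises it or staff come across it |
| Assessments (d.2.1, e) | No disclosure or study-harm question among the topics listed |
| Program Evaluation Survey (h.2.b) | No such topic listed; written comments could carry it unprompted, once, at the end of the study |
| App usage tracking (d.2.1, e) | Records use, not the reason use stops |
| PI monthly review (section 4) | Reviews what the other sources supply |

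No row is a scheduled question to the participant about this harm.

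**5. Who is at risk.** Section d.2.1 has text reminders going to both LN and EP participants, and Aim 4 treats both as app users. The relevant group is the whole trial, about 240 enrolled, not the LN arm alone.

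**The case against.** The strongest reply has four parts.

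- *The instruments cannot be seen.* The topics listed are category names, and an item on privacy could sit under attitudes or acceptability. This stands. The gap is in the measures described, and if an item exists the sponsor need only cite it.
- *The monitoring plan is not bare.* It includes staff training, weekly interviewer contact with the PI (section 3), monthly review, IRB contact after a breach, and the f.2.b safeguards. Earlier focus group participants also voiced no worry, or little, about the program revealing their status. This stands as evidence of care and low expected risk. But prevention and opinion before use do not measure what happens in use.
- *The zero count is only one of two reasons.* This also stands. The judgement of minimal risk would remain without it, and nothing here argues against PI-led monitoring.
- *The c.5 sentence is background, not a hypothesis.* True, so the point does not rest on it.

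Three stronger readings are tempting and are not supported. A reader might infer that 77 is an error; section 4 never says that 77 people received LN. A reader might stretch the 12-week limit to nine months and quote a number of LN participants who could be harmed. That needs a constant hazard that the documents do not give, and it concerns any adverse event, not app disclosure. A reader might also conclude that disclosure will cause drop-out or low app use; that is possible, but nothing in the documents shows it.

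**Conclusion.** The point holds in a limited form. Section 4 leans in part on a pilot in which 51 of 77 people were randomized to LN, with assessments to 12 weeks. For any adverse event on LN over that time, zero in 51 excludes risks above 5.7% (one-sided 95%), not 3.8%. For privacy harm through the app or texts, the pilot gives no information. The trial as described has no systematic way to learn of such harm when it happens away from staff.

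This rests on three assumptions: that the pilot RCT did not use the app, inferred from Aim 1; that the listed topics represent the instruments fairly; and, for 5.7%, that all 51 were observed throughout. It does not show that harms are likely or that participants are unprotected. The change is a cheap improvement to how harm is ascertained.

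**What to change.** 1. Check the instruments in the IRB application. If they already ask about unwanted disclosure and other study-related problems, cite the items in section 4 and stop at step 4.
2. If not, add two or three fixed items to the existing 3, 6 and 9 month assessments in both arms: whether anyone learned or suspected private health information through the study phone, app, texts or calls; whether harm followed; and any other problem linked to the study. Give them by ACASI or, at phone follow-up, after the f.2.b privacy check.
3. Send positive answers to the PI's log for the monthly review, and report counts by arm.
4. In section 4, state that 51 of the 77 were randomized to LN and followed for 12 weeks, and that the pilot does not address app or text risks. Do not assert what device or messages the pilot used unless the sponsor can confirm it.
5. Put no item naming HIV status in the monthly app or phone pill count. Any prompt there should use neutral wording consistent with f.2.b, or the question itself could disclose.

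Cost: slightly longer interviews, an IRB amendment, and a harm count that will look less favourable than one from staff reports alone. No new visit is needed.
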